### Reasons for this Amendment

The primary reasons for this amendment are:

- 1. To update the design and size of the study to remove the study expansion phase, due to difficulties in recruitment in the study.
- 2. To restrict individual patient's follow-up to a maximum of 25 months (including clarification of reasons for earlier withdrawal), which is the follow-up required for the study primary endpoint. A longer follow up was envisaged for efficacy assessment but has a limited value considering the reduced sample size.
- 3. To update the study objectives to formally list the biodistribution of Betalutin in combination with rituximab (RTX) and to establish a recommended dose of Betalutin in combination with RTX for phase 2 studies as objectives and to describe the endpoints for pharmacokinetics, pharmacodynamics and biodistribution studies. This is to rectify an oversight in the initial protocol.

### Other reasons for the amendment are:

- 4. Details of study personal have been updated where appropriate
- 5. Correction of typographical errors have been made, where relevant. Section headings and formatting were updated, where applicable.
- 6. A clarification was added that tumour scans must be kept at the study site for potential review by the Sponsor but it is not mandatory to send them for storage.

Changes made to the body text have been reflected in the synopsis.

# **Protocol Amendment Summary of Changes Table**

DOCUMENT HISTORY						
Document	Date					
Version 1.0	6 th February 2018					
Version 2.0	16 th October 2018					
Version 3.0	19 th December 2018					
Version 4.0	04 October 2021 (this document)					

The changes are individually listed in Appendix 6.

# 1. Protocol Summary

# 1.1. Synopsis

Investigational drug	Betalutin® (lutetium [177Lu] lilotomab satetraxetan)
	Lilotomab
	Rituximab
Protocol number	Version 4.0_04 Oct 2021
Sponsor	Nordic Nanovector ASA, Oslo, Norway
Study phase	Phase 1b
Study title	A phase 1b open-label study of Betalutin in combination with rituximab in patients with relapsed/refractory follicular lymphoma (Archer-1)
Short title	Study of safety and efficacy of Betalutin and rituximab in patients with FL
Background/ Rationale	Indolent Non-Hodgkin lymphoma (iNHL) remains largely incurable, despite good response rates to first line therapy, and nearly all patients eventually relapse. As patients relapse, they become resistant or refractory to commonly used therapies, including rituximab (RTX) and alkylating agents, and their prognosis worsens, especially for those who are no longer able to tolerate chemotherapy. New therapies with different mechanisms of action are thus needed to improve outcomes in patients who have recurrent NHL following RTX or other anti-CD20-based therapy.
	CD37 is highly expressed in B-cell NHL and is an attractive target for treatment. Betalutin is a novel CD37-directed antibody radionuclide conjugate (ARC) that has demonstrated clinical activity and is well-tolerated in patients with relapsed iNHL. Preliminary data from a phase 1/2 clinical study (LYMRIT 37-01) show that Betalutin is active as a single agent, and has a favourable toxicity profile, with reversible neutropenia and thrombocytopenia being the main toxicities reported [Kolstad, 2017].
	RTX-based combination regimens are a mainstay of NHL treatment. Recently, preclinical data were reported demonstrating that sequential therapy with Betalutin followed by RTX significantly reduced tumour growth and improved overall survival in a murine model of NHL, suggesting synergism between the 2 agents [Repetto-Llamazares, 2016]. One mechanism may be via increased surface CD20 expression following Betalutin exposure [Repetto-Llamazares, 2015]. These data suggest a potential immunomodulatory role of Betalutin in modulating CD20 expression on NHL cells, which may potentially enhance the efficacy of RTX, and support evaluating the combination of Betalutin followed by RTX in patients with recurrent NHL.
	This phase 1b study will investigate the dosing of Betalutin in combination with RTX, whereby RTX is given shortly following Betalutin to capitalise on potential enhanced CD20 expression after Betalutin administration. One phase 2 study evaluating short course cyclophosphamide, hydroxydaunorubicin, oncovin and prednisone (CHOP)-RTX chemotherapy followed by 90Y-ibritumomab tiuxetan (Zevalin®) in treatment-naïve

follicular lymphoma (FL) patients has been reported [Jacobs, 2008]. Fifty-five patients received 3 courses of CHOP-RTX followed by Zevalin® once haematologic recovery was attained. One week following Zevalin administration, four additional weekly doses of RTX were given. The incidences of grade 3/4 neutropenia and thrombocytopenia were 51% and 44% respectively, consistent with previously reported data (prescribing information for RTX), and all patients had full haematologic count recovery by 12 weeks post-Zevalin. The use of RTX six months following Zevalin® administration in previously untreated high tumour burden FL patients was reported to convert all partial responses (PRs) to complete responses (CRs) in one study [Rajguru, 2014], but the optimal duration of rituximab therapy is unknown. Combining Betalutin with RTX may be attractive to patients due to a favourable dosing schedule, and potential for maintaining a good quality of life. We hypothesise that combining Betalutin with RTX could enhance both the response rates and the durability of responses in patients with recurrent FL.

This protocol describes a Phase 1b, open-label, single-arm, dose escalation study of Betalutin followed by RTX in patients with previously treated FL. The purpose of this study is to characterise the safety, tolerability, pharmacokinetics, pharmacodynamics and antitumour activity of Betalutin in combination with RTX.

# Objectives (key primary and secondary)

### **Primary**

To evaluate the safety and tolerability of Betalutin in combination with RTX

#### Secondary

- To establish a recommended dose of Betalutin in combination with RTX for phase 2 studies in NHL patients
- To evaluate the preliminary anti-tumour activity of combination treatment based on Investigator assessment of tumour response rates
- To evaluate the duration of tumour control in patients receiving Betalutin in combination with RTX
- To investigate the immunogenicity of Betalutin in combination with RTX

# Endpoints (key primary and secondary)

#### **Primary**

 Frequency and severity of adverse events (AEs), serious adverse events (SAEs) and changes in laboratory values graded according to Common Terminology Criteria for Adverse Events (CTCAE) version 4.03

#### **Secondary**

- Responses (overall response rate [ORR], CR, PR, stable disease [SD], progressive disease [PD]) as per Cheson 2014
- Duration of response (DoR)
- Progression free survival (PFS)
- Time to progression (TTP)
- Overall survival (OS)
- Monitoring of the anti-drug antibody (ADA) response towards lilotomab, Betalutin and/or RTX

### Study design

This protocol describes a Phase 1b open-label, single-arm dose escalation study to investigate the activity and safety and preliminary efficacy of Betalutin combined with RTX in patients with FL who have received one or more prior therapies.

All patients will receive a single intravenous (i.v.) dose of RTX (375 mg/m^2) on Day -14, and then sequential iv administration of lilotomab (40 mg) followed by Betalutin (10 or 15 MBq/kg) within 4 hours on Day 0. Patients will then be administered RTX (375 mg/m^2) i.v. on Days 7, 14, 21 and 28.

Two cohorts of 3-6 patients will be evaluated for dose limiting toxicity, in a 3+3 escalation pattern, to determine the Betalutin dose for future phase 2 studies in NHL.

Patients will undergo clinical and laboratory assessments during screening/baseline and periodically during treatment. PET/CT and CT (or MRI) imaging will be performed at baseline and then at 3 and 6 months. CT with contrast (or MRI) will be performed at 12, 18, 24 months or until disease progression or withdrawal from the study for any other reason (whichever comes first).

Patients who achieve SD, CR or PR on their Month 3 imaging scan will be administered maintenance RTX 375 mg/m^2 i.v. or 1400 mg s.c. every 3 months for up to 2 years (8 infusions in total), or until disease progression or withdrawal from the study for any other reason (whichever comes first).

#### **Population**

FL patients who have received one or more prior therapies

# Inclusion/ exclusion criteria

#### **Inclusion:**

Patients are eligible to be included in the study only if all of the following criteria apply:

- 1) Patient must be  $\ge 18$  years at the time of signing the informed consent
- 2) A pre-study Eastern Cooperative Oncology Group (ECOG) performance status of 0-2
- 3) Histologically confirmed diagnosis (by 2008 World Health Organisation [WHO] classification) of iNHL FL (grade 1, 2 or 3a)
- 4) At least one (but not more than 3) prior regimens with an anti-CD20 antibody (alone or in combination with chemotherapy), with documented relapsed, refractory disease (must not be anti-CD20 antibody-refractory) or PD
- 5) Presence of at least one bi-dimensionally measurable lesion by CT or MRI: longest diameter (LDi) >1.5 cm for a nodal lesion; LDi >1.0 cm for an extranodal lesion within 28 days prior to start of treatment
- Normal organ and bone marrow function defined as:
  - a) Absolute neutrophil count  $\geq 1.5 \times 10^9/L$ ;
  - b) Platelet count  $\geq 150 \times 10^9/L$ ;
  - c) Haemoglobin ≥9 g/dL;
  - d) Total bilirubin ≤1.5 x upper limit of normal (ULN) (except patients with documented Gilbert's syndrome [<3.0 mg/dL]);
  - e) Liver enzymes: Aspartate transaminase (AST); Alanine transaminase (ALT) or Alkaline phosphatase (ALP) ≤2.5 x ULN (or ≤5.0 x ULN if liver involvement by primary disease);
  - f) Adequate renal function as demonstrated by a serum creatinine within the upper limit of normal range
- 7) Bone marrow involvement by lymphoma <25%
- 3) Life expectancy >3 months
- 9) Negative hepatitis B, hepatitis C and human immunodeficiency virus (HIV) screening tests
- 0) Undetectable human anti-murine antibodies (HAMA) at screening

- 11) Women of childbearing potential must:
  - a. have a negative serum pregnancy test at screening
  - b. understand that the study medication is expected to have teratogenic risk
  - c. agree to use, and be able to comply with, highly effective method of birth control with a Pearl-Index  $\leq 1\%$

Contraception is required without interruption, from 4 weeks before starting study drug, throughout study drug therapy and for 12 months after end of study drug therapy, even if she has amenorrhea

- 12) Male patients must agree to use condoms during intercourse throughout study drug therapy and for 12 months after end of study drug therapy
- 13) The patient is willing and able to comply with the protocol, and agrees to return to the hospital for follow-up visits and examination
- 14) Capable of giving signed informed consent which includes compliance with the requirements and restrictions listed in the informed consent form (ICF) and in this protocol

#### **Exclusion:**

Patients are excluded from the study if any of the following criteria apply:

- 1. Previous haematopoietic stem cell transplantation (autologous and allogenic)
- 2. Evidence of histological transformation from FL to diffuse large B-cell lymphoma (DLBCL) at time of screening
- 3. Previous total body irradiation
- 4. Chemotherapy, immunotherapy, or investigational therapy within 28 days before the start of study drug administration (corticosteroid treatment at doses of ≤20 mg/day, topical or inhaled corticosteroids, granulocyte colony-stimulating factor [G-CSF] or granulocyte-macrophage colony-stimulating factor [GM-CSF] are permitted up to 2 weeks prior to start of study treatment) or failure to recover from AEs associated with prior treatment
- 5. Previous treatment with radioimmunotherapy
- 6. Patients who are receiving any other investigational medicinal products
- 7. Known or suspected central nervous system (CNS) involvement of lymphoma
- 8. History of a previous treated cancer except for the following:
  - a. adequately treated local basal cell or squamous cell carcinoma of the skin
  - b. cervical carcinoma in situ
  - c. superficial bladder cancer
  - d. localised prostate cancer undergoing surveillance or surgery
  - e. localised breast cancer treated with surgery and radiotherapy but not including systemic chemotherapy
  - f. other adequately treated Stage 1 or 2 cancer currently in CR
- 9. Pregnant or lactating women
- 10. Exposure to another CD37 targeting drug
- 11. A known hypersensitivity to RTX, lilotomab, Betalutin or murine proteins or any excipient used in rituximab, lilotomab or Betalutin
- 12. Receipt of live, attenuated vaccine within 30 days prior to enrolment
- 13. Evidence of severe or uncontrolled systemic diseases:
  - uncontrolled infection including evidence of ongoing systemic bacterial, fungal, or viral infection (excluding viral upper respiratory tract infections) at the time of initiation of study treatment
  - b. Pulmonary conditions e.g. unstable or uncompensated respiratory disease

	
 
c. Hepatic, renal, neurological, or metabolic conditions - which in the opinion of the Investigator would compromise the protocol objectives
 
d. Psychiatric conditions e.g. patients unlikely to comply with the protocol, e.g. mental condition rendering the patient unable to understand the nature, scope, and possible consequences of participating in the study
 
e. History of erythema multiforme, toxic epidermal necrolysis or Stevens-Johnson syndrome
 
f. Cardiac conditions, including: 
 
i. history of acute coronary syndromes (including unstable angina)
 
ii. class II, III or IV heart failure as defined by the New York Heart Association (NYHA) functional classification system
 
iii. known uncontrolled arrhythmias (except sinus arrhythmia) in the past 24 weeks
 
 
 

Sample size	6 to 12 patients will be enrolled
Treatment groups, dose, route of administration, treatment regimen	Single arm study with patients to be treated with the following study drugs: Rituximab - 375 mg/m  to be administered by i.v. infusion through dedicated line at Days -14, 7, 14, 21 and 28. Patients who achieve SD, CR or PR on their Month 3 imaging scan will be administered maintenance RTX 375 mg/m  i.v. or 1400 mg s.c. every 3 months for up to 2 years (8 infusions in total), or until disease progression or withdrawal from the study for any other reason (whichever comes first).
	Lilotomab – 40 mg to be administered by i.v. infusion at Day 0
	Betalutin – 10 or 15 MBq/kg to be administered by slow bolus i.v. injection within 4 hours following lilotomab on Day 0
Efficacy assessment(s)	PET/CT and CT (or MRI) imaging will be performed at baseline and then at 3 and 6 months. CT with contrast (or MRI) will be performed at 12, 18, 24 months or until disease progression or withdrawal from the study for any other reason (whichever comes first)  Tumour response will be determined locally according to Recommendations for Initial
	Evaluation, Staging and Response Assessment of Hodgkin and non-Hodgkin Lymphoma [Cheson, 2014]
Safety assessment(s)	In the treatment phase vital signs, electrocardiogram (ECG), physical examination, haematology, serum biochemistry and all AEs are collected at specified time points.
	Two cohorts of 3-6 patients will be initially evaluated for dose limiting toxicity before determining the subsequent Betalutin dose for the remainder of the study. Dose-escalation decisions will be made by the Investigator(s) and Sponsor following review of the safety data once haematologic recovery has occurred.
	After the last dose of rituximab, vital signs, ECG (final visit only), physical examination, haematology, serum biochemistry, Adverse Drug Reaction (ADR) and Adverse Events of Special Interest (AESI) will be collected at an end of study visit that will occur at least 28 days post last administration of study treatment. Patients in survival follow-up at time of Protocol v4.0 approval can have the EOS visit at their next scheduled visit or an earlier convenient time point.
Pharmacokinetics and biodistribution	Total radioactivity measurements in blood will be performed at certain intervals until Day 28. Mandatory at Radium Hospital (Oslo, Norway) only, otherwise optional. Patients will undergo SPECT imaging at certain time points in order to measure distribution of

	Betalutin in the body and calculate absorbed radiation dose to target organs/tissues and tumours.
Biomarker assessments	Biomarkers assessments including CD20 and CD37 expression in tumour tissue biopsy and immunophenotyping of circulating lymphocyte subsets (absolute cell counts), will be performed at various time points throughout the study
Other biomarker studies on additional samples	Biomarkers including but not exclusive to MRD (blood) and gene expression changes related to disease treatment in tumour tissue (archival or newly collected biopsy at screening, relapse or disease progression), will be assessed at various time points throughout the study. Patient's major histocompatibility complex (MHC) class I/II haplotype will be defined using peripheral blood (DNA) or saliva (DNA). Anti-tumour T-cell responses will be explored by flow cytometry after co-culture of peripheral mononuclear cells (blood) and autologous lymphoma cells (biopsy and/or needle aspirate), and other biomarkers at selected time points throughout the study at Radium Hospital (Oslo, Norway) only.
Statistical methods and data analysis	The safety analysis population will include all patients who received at least one dose of any study drug.
	The intent-to-treat (ITT) population will consist of all patients who were enrolled and treated with lilotomab/Betalutin, regardless if RTX therapy was initiated. The number and percentage of patients with each response and overall (complete + partial responders) will be presented for each time point for the ITT population.
	Pharmacokinetic, biodistribution and biomarker exploratory analyses will be described in the statistical analysis plan finalised before database lock.
Key dates	The start date of the study (first patient included) was in October 2018.
	The expected accrual time is 18 months.
	Patients will be followed up for up to 25 months (End of study visit) after Betalutin administration.
	Patients in survival follow at time of Protocol version 4.0 approval can have the EOS visit at their next scheduled visit or an earlier convenient time point

CONFIDENTIAL

Protocol Study Number: LYMRIT-37-07

Version 4.0\_04 Oct 2021

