## 6.1. Dosing regimen

Two cohorts of 3-6 patients will initially be evaluated. The first cohort of 3 patients will be treated with a single i.v. dose of RTX (375 mg/m²) on Day -14, and then on Day 0, sequential i.v. administration of lilotomab (40 mg) followed by Betalutin (10 MBq/kg) within 4 hours on Day 0. The patients will then be administered RTX (375 mg/m²) i.v. on Days 7, 14, 21 and 28.

Patients must have received all doses of study drug and have had an adequate period of follow-up (i.e. having achieved haematological recovery to  $\leq$  grade 2) to be considered evaluable for a dose escalation decision or to determine the dose for further Phase 2 studies following enrolment of the second cohort of 3-6 patients. The dose for the next cohort of 3 patients will be determined by the Investigator(s) and Nordic Nanovector study personnel via teleconference. Decisions will be based on a review of all safety data (clinical and laboratory) and are outlined as follows:

- 1. If 0/3 patients experience a DLT (defined below), the next cohort of 3 patients will receive lilotomab 40 mg plus Betalutin 15 MBq/kg prior to RTX on Day 0.
- 2. If 1/3 patients experience a DLT, then 3 more patients will be enrolled in the current cohort at this dose level (Betalutin 10 MBq/kg).
- 3. If 2/3 patients experience a DLT, then subsequent Betalutin/lilotomab and/or RTX dosing will be determined by the Investigator(s) and Sponsor after a review of the safety data.
- 4. If 1/6 patients experience a DLT, the next cohort of 3 patients will be treated with Betalutin 15 MBq/kg.
- 5. If 0/3 patients receiving Betalutin 15 MBq/kg experience a DLT, the remainder of the patients in the study will continue to be treated with Betalutin 15 MBq/kg.
- 6. If 1/3 patients experience a DLT, then 3 more patients will be enrolled at this dose level (Betalutin 15 MBq/kg).
- 7. If 1/6 patients receiving Betalutin 15 MBq/kg experience a DLT, the dose for further Phase 2 studies will be Betalutin 15 MBq/kg.
- 8. If 2/6 patients experience a DLT, then 3 more patients will be treated at the lower Betalutin dose (10 MBq/kg).
- 9. The final recommendation for Betalutin/lilotomab dosing for further Phase 2 studies will be determined by the Investigator(s) and Sponsor after a review of the available safety data.

DLT is defined as:

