Section 4.4 Patient and Study Completion  Approximately 25 patients will be screened to achieve 20-25 patients assigned to study treatment and evaluable.	Section 4.4 Patient and Study Completion  Approximately 25 10-15 patients will be screened to achieve 20- 256-12 patients assigned to study treatment and evaluable.	1
Section 4.5 End of Study Definition  The end of study for all patients will be the date of the last visit upon completion of the follow-up period (5 years after receiving their Betalutin	Section 4.5 End of Study Definition  The end of study for all patients will be the date of the last patient last visit upon completion of their end of study visit follow up period (5 years 25 months after receiving their Betalutin treatment if ending study	2

Modified or Additional Wording	Justification
treatment per protocol, or after disease progression or until discontinuation withdrawal from the study for any other reason, (whichever comes first) or if the study is terminated early.	
Section 6.1 Dosing Regimen	1
Patients must have received all doses of study drug and have had an adequate period of follow-up (i.e. having achieved haematological recovery to ≤ grade 2) to be considered evaluable for a dose escalation decision or to continue to be treated with Betalutin 15 MBq/kg determine the dose for further Phase 2 studies following enrolment of the second cohort of 3-6 patients.	
Section 6.1 Dosing Regimen	1
7. If 1/6 patients receiving Betalutin 15 MBq/kg experience a DLT, the remainder of the patients in the study will continue to be treated with dose for further Phase 2 studies will be Betalutin 15 MBq/kg.	
8. If 2/6 patients experience a DLT, then 3 more patients will be treated at the lower Betalutin dose (10 MBq/kg).	
9. Subsequent The final recommendation for Betalutin/lilotomab dosing for further Phase 2 studies will be determined by the Investigator(s) and Sponsor after a review of the available safety data.	
Section 7.2 Patient Withdrawal/Discontinuation from the Study	2

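### Section 6.1 can lead to 15 evaluable patients against a stated maximum of 12, and rule 5 still assigns an undefined remainder of patients (minor)

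*Combined protocol and SAP*

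**What the plan says.** The Synopsis (Section 1.1, Sample size) states "6 to 12 patients will be enrolled". Sections 4.1 and 4.4 give the same range for evaluable patients, and Section 10.1 calls it a reasonable size. Section 4.4 plans for approximately 10 to 15 patients screened.

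Section 6.1 sets two cohorts of 3 to 6 and lists nine rules. Four matter here:

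- Rule 5 (0/3 with a DLT at 15 MBq/kg): "the remainder of the patients in the study will continue to be treated with Betalutin 15 MBq/kg".
- Rule 7: "If 1/6 patients receiving Betalutin 15 MBq/kg experience a DLT, the dose for further Phase 2 studies will be Betalutin 15 MBq/kg".
- Rule 8: "If 2/6 patients experience a DLT, then 3 more patients will be treated at the lower Betalutin dose (10 MBq/kg". It sets no condition on how many patients have already been treated at 10 MBq/kg.
- Rule 9: "The final recommendation for Betalutin/lilotomab dosing for further Phase 2 studies will be determined by the Investigator(s) and Sponsor", after a safety review.

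The evaluability sentence in the same section looks ahead "to determine the dose for further Phase 2 studies following enrolment of the second cohort of 3-6 patients". The first reason given for version 4.0 is "To update the design and size of the study to remove the study expansion phase".

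**The concern.** Two parts of the current Section 6.1 do not fit the reduced design.

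First, rule 8 tells sites to treat three more patients at the lower dose whether that dose has had three patients or six. With six, following the rule as written takes the trial past its stated maximum.

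Second, rule 5 covers a clean second cohort, yet it gives no endpoint. It refers to further patients in the study, when the expansion phase that would have supplied them has been removed. Rule 7, for the neighbouring outcome of 1/6, ends in a phase 2 dose. The Synopsis (Safety assessment(s)), Section 4.1 and Section 4.2 also still speak of choosing a dose for the rest of the study, whereas the Synopsis Study design text now speaks of the dose for future phase 2 studies.

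What is at stake is whether a site knows how many patients to enrol after each outcome, and whether the size stated in the protocol covers every path its own rules allow.

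**Working it through.** **Stated size.** Two cohorts of 3 to 6 give 2 × 3 = 6 to 2 × 6 = 12. This reproduces the stated range. There is no power calculation to check.

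**Counting the paths.** Counts are of evaluable patients. Section 7.3 allows a non-evaluable patient's place to be filled, so enrolled numbers can be higher. Rules 2 and 6 add three patients after 1/3; rules 1 and 4 escalate after 0/3 or 1/6. The paths that escalate and end in rule 5, 7 or 8 are:

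| DLTs at 10 MBq/kg | DLTs at 15 MBq/kg | Rule | Total evaluable |
|---|---|---|---|
| 0/3 | 0/3 | 5 | 3 + 3 = 6, plus remainder |
| 0/3 | 1/6 | 7 | 3 + 6 = 9 |
| 0/3 | 2/6 | 8 | 3 + 6 + 3 = 12 |
| 1/6 | 0/3 | 5 | 6 + 3 = 9, plus remainder |
| 1/6 | 1/6 | 7 | 6 + 6 = 12 |
| 1/6 | 2/6 | 8 | 6 + 6 + 3 = **15** |

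All other paths have more DLTs. They stop the escalation with 3 to 12 patients treated, and no numbered rule then fixes a further number. Only the last row of the table exceeds 12. If rule 8 applies only when three patients have been treated at 10 MBq/kg, that row becomes 6 + 6 = 12, and the maximum over all paths is 12.

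**How likely the 15-patient path is.** Let p be the DLT rate at 10 MBq/kg and q the rate at 15 MBq/kg. The path needs 1/3 then 0/3 at 10 MBq/kg, followed by 1/3 then 1/3 at 15 MBq/kg:

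P(15) = 3p(1−p)^5 × [3q(1−q)^2]^2

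The documents give no DLT rate for the combination, so p and q are assumptions. Section 2.2.2.1 offers a partial guide for q. Of 36 patients given single-agent 15 MBq/kg, two had grade 4 neutropenia and two had grade 4 thrombocytopenia for more than 7 days. That is 2 to 4 of 36 (6% to 11%), depending on overlap, and covers only part of the DLT definition.

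- p = 0.05, q = 0.11: 0.1161 × 0.2614² = 0.1161 × 0.0683 = 0.0079, or 0.8%.
- p = 0.10, q = 0.20: 0.1771 × 0.384² = 0.1771 × 0.1475 = 0.0261, or 2.6%.
- Maximum at any rates: the first factor peaks at p = 1/6 (0.2009) and the second at q = 1/3 ((4/9)² = 0.1975), giving 0.0397, or about 4%.

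**Rule 5.** Three patients have been treated at 15 MBq/kg, and a cohort holds 3 to 6, so the remainder is 0 to 3. Totals are then 6 to 9 if the first cohort had three patients, and 9 to 12 if it had six. All stay within 12. The evaluability sentence sets the phase 2 dose once the second cohort is enrolled, which points to a remainder of 0; rule 5's own words say that treatment continues. For the pair p = 0.05, q = 0.11, the chance of ending at rule 5 is (1−p)^3(1−q)^3 + 3p(1−p)^5(1−q)^3 = 0.604 + 0.082 = 0.686, so it is the commonest ending at low toxicity.

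**Limit of these probabilities.** They run from the first patient. The study started in October 2018, and version 4.0 is dated 4 October 2021, about three years later. The documents do not say how far escalation had gone, so none of these figures is the chance of meeting the problem under version 4.0.

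**The case against.** The best defence of rule 8 is convention. The protocol calls for a 3+3 pattern with cohorts of 3 to 6, and under that pattern the lower dose is filled only to six, which gives 12. Sections 4.1 and 4.4 use planned and approximate numbers, and the investigators and sponsor review safety before each cohort. This makes it likely that 12 was intended. It does not supply the missing condition: rule 8 states none, Section 6.1 says the two cohorts are evaluated initially, and rule 9 settles the final recommendation, not whether rule 8's three patients are treated.

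Three stronger readings are tempting and should be set aside.

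- A reader might infer that rule 5 leaves room for up to six more patients, since 12 − 6 = 6, and so nine at 15 MBq/kg. The Synopsis and Section 6.1 both describe cohorts of 3 to 6, so six at that dose is the consistent ceiling. Nor is the remainder strictly impossible, since up to three would fit. The accurate word is undefined.
- A reader might infer a loss of precision about toxicity. With no DLT in three patients the exact one-sided 95% upper limit is 1 − 0.05^(1/3) = 63%; with six it is 1 − 0.05^(1/6) = 39%. But stopping a 3+3 cohort at 0/3 gives 63% however rule 5 is worded. That is a property of small cohorts.
- A reader might infer that the trial was likely to overshoot. The 4% is a ceiling counted from the start of the study.

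The change list in Appendix 6 is not needed as evidence: current rules 5 and 7 differ on their face.

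**Conclusion.** Wrong as written, and minor. On one path (1/6 at 10 MBq/kg, then 2/6 at 15 MBq/kg), rule 8 read literally produces 15 evaluable patients, three above the maximum given in four places. The count is exact given that reading. The probability of at most about 4% assumes independent outcomes and the same DLT rate for every patient at a dose. Rule 5 leaves 0 to 3 patients unassigned, with 0 the natural reading. No test, power or error rate depends on either point.

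**What to change.** - **Rule 8:** apply it only if three patients have so far been treated at 10 MBq/kg. If six have been treated there, enrol no more and go to rule 9. The maximum stays at 12. Alternatively, keep the rule, restate the maximum as 15 evaluable patients in Sections 1.1, 4.1, 4.4 and 10.1, and raise the screening number, because 15 evaluable would use up the top of the approximate 10 to 15.
- **Rule 5:** replace the remainder clause with a stated outcome, as rule 7 has. Either 15 MBq/kg becomes the phase 2 dose, subject to rule 9, or three more patients are enrolled to fill the cohort to six. The choice belongs to the sponsor and investigators.
- **Elsewhere:** bring the remainder wording in the Synopsis (Safety assessment(s)) and Sections 4.1 and 4.2 into line with the Synopsis Study design text.

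The cost is protocol wording only. Limiting rule 8 adds no patients and removes three on one path. Filling the 15 MBq/kg cohort under rule 5 adds three and stays within 6 + 6 = 12.
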